Title: Pragmatic Cyclical Lower Extremity Exercise Trial for Parkinson's disease

NCT #: NCT04000360

Document Date: November 9, 2021

Title: Pragmatic Cyclical Lower Extremity Exercise for Parkinson's Trial

PI: [name]

Date Modified: 11/9/2021

SPECIFIC AIMS

An unmet need in the treatment of Parkinson's Disease (PD) is identification of an effective disease-modifying intervention (e.g. pharmaceutical, surgical or behavioral).^{1,2} Increasing evidence, from our laboratory³⁻⁷ and others,⁸⁻¹⁰ coupled with our recently completed NIH-sponsored randomized controlled trial (RCT), *CYClical Lower Extremity exercise for Parkinson's trial (CYCLE)*, indicates high intensity aerobic exercise is a candidate to alter PD progression. CYCLE trial data demonstrate that exercise delivered in a controlled, supervised laboratory setting results in global improvements in motor and non-motor function. Global improvements were preserved following exercise cessation, suggesting exercise is likely enhancing CNS function.^{3,4,7} The precise mechanism underlying improved post-exercise motor function in PD is unknown. Our imaging data^{5,6,11} and others^{12,13} suggest a plausible mechanism is improved thalamo-cortical connectivity, facilitated through elevation of neurotrophic factors.^{14,15} A multi-site pragmatic RCT is proposed, in which PD patients complete the CYCLE protocol at home, to address the following questions: 1) What are the disease-altering capabilities of a PD-specific long-term, high intensity aerobic exercise intervention? 2) What are the relationships of patients' phenotype and exercise performance variables to PD progression within such an exercise program? Based on preliminary data, we hypothesize that long-term high-intensity aerobic exercise slows PD progression relative to Usual and Customary Care (UCC). In sum, approximately 250 mild to moderate PD patients from Cleveland Clinic and University of Utah will be randomized to a high-intensity home exercise or a UCC group. The CYCLE protocol, involving aerobic intensity between 60-80% of heart rate reserve with a target cadence between 80-90 RPMs, will be delivered to the patients' home via the commercially available *Peloton Cycle*. The exercise group will be asked to cycle 3x/week for 12 months. The UCC group will be instructed to engage in their normal activities. The Movement Disorder Society Unified Parkinson's Disease Rating Scale (MDS-UPDRS III) will be used to evaluate disease progression or rate of physical decline. Blinded MDS-UPDRS III evaluations will be completed at: enrollment, 6 and 12 months. Biomechanical iPad assessments of motor and non-motor function¹⁶⁻¹⁹ will be completed at each time point; thus augmenting clinical outcomes to provide a comprehensive understanding of the effects extended exercise on specific aspects of PD motor control and executive function. Overall activity levels will be monitored for both groups via a wearable sensor.

Aim 1: To determine the disease-altering effects of a home-based high-intensity aerobic exercise program.

12-month MDS-UPDRS III rate of decline while off medication will serve as the primary outcome.

Hypothesis: Those in the high intensity exercise group will have a significantly smaller one-year rate of decline in MDS-UPDRS III scores compared to the UCC group.

Aim 2: To determine the effects of a home-based aerobic exercise program on upper and lower extremity function using biomechanical outcomes.

Our Nine Hole Peg Test (9HPT),¹⁹ gait speed¹⁹ and Timed Up and Go (iTUG)^{20,21} iPad modules will be used to quantify upper and lower extremity function.

Hypothesis: Performance on 9HPT, gait speed and iTUG will show significantly slower rates of decay over 12 months for those in the exercise group compared to the UCC group.

Aim 3: To determine the effects of a home-based aerobic exercise program on non-motor function.

Non-motor assessments will be evaluated using our iPad-based tests of processing speed (Processing Speed Test^{19,22}), working memory and set switching (Trail Making Test A & B).

Hypothesis: Rates of decline in executive functions from enrollment to 12 months will be significantly less in the exercise group compared to the UCC group.

Aim 4: To develop a prognostic model to predict 12-month MDS-UPDRS III decline for patients participating in a home-based high-intensity aerobic exercise program.

PD demographics (age, gender, disease duration, primary symptoms, age of onset, etc.) coupled with exercise performance variables (compliance, duration, cadence, heart rate, power, heart rate variability) will be used to predict 12-month change in MDS-UPDRS III scores among the exercise cohort.

Hypothesis: Demographics, baseline PD status and comorbidities, and exercise performance will predict 12-month PD progression. Time in target heart rate zone and cadence, particularly, will notably improve predictions over those from baseline measures only.

APPROACH

To test the hypothesis that high intensity exercise completed by PD patients in their the home can alter disease progression, we will consent and randomize approximately 250 CC and UU PD patients to home-based high-intensity aerobic exercise or UCC within 3 years, and monitor group exercise parameters, activity levels, and PD progression in both groups. The trial will be conducted under Data Safety Monitoring Board (DSMB) oversight.

[figure not shown]
Participant Recruitment, Screening and Randomization:

CC's Center for Neurological Restoration (CNR) manages 6,000+ PD patients; each patient typically has semi-annual neurology visits which include a complete MDS-UPDRS III evaluation. UU's Movement Disorders Program manages 2,000+ PD patients. Their respective Directors, Drs. [name] (Cleveland) and [name] (Utah), will lead their medical teams to screen in recruiting for this project and will complete MDS-UPDRS III clinical evaluations, blinded to group assignment. The pragmatic clinical trial design, with exercise at home and relatively few visits to the study site, will minimize travel burden, easing recruitment and facilitating recruitment of a racially and socio-economically diverse patient group.²³ It is anticipated that study sites will enroll an equal number of participants. Adults with idiopathic PD who meet inclusion criteria and cleared for exercise will

be randomized to either the home exercise or UCC group, using a permuted block randomization stratified by site, with random block sizes of 8, 10, or 12 for the first 8 blocks at each site, and 4, 6, or 8 subsequently, preloaded into a secure and shared RedCap electronic data management system developed at CC. Both sites have effectively utilized RedCap across in previous multi-site clinical trials,²⁴⁻³¹ and clinical programs. Figure 1 depicts study flow. Total study participation time is projected to be 12.5 months, including ~2.5 weeks for cycle delivery and completion of initial Comprehensive Assessments (On-/Off- meds).

As shown in Figure 1, three Comprehensive assessments of motor and non-motor function will be conducted for all participants. Comprehensive (90 mins) assessments (Table 1) will be overseen by Drs. [name] and [name], and will be completed at project enrollment (On- and Off-medication), 6 months (Off-medication), and 12 months (Off-medication). Visit windows will be within \pm 10 days of their nominal dates. Participants will be reimbursed for time and travel expenses of \$50 for each assessment. All clinical and self-report data will be entered into the RedCap database (see Data and Safety Monitoring). Each site's biomechanical data from the iPad will be uploaded securely, with encryption, to the CC HIPAA-compliant cloud instance (ClearData), processed in the cloud, and integrated into the [name] lab's on-premises, firewall protected, server.

Asking participants to withhold medication for Off-state examinations imposes a burden, but the Off-state (12 hours off meds) will increase insight into the direct effect of exercise on PD itself. Since medication changes are frequent with PD and often result in symptomatic fluctuations, the Off-state provides a more reliable, less confounded time comparisons. Medication reconciliation will be completed at each examination, and levodopa equivalent daily doses (LEDDs) will be determined and utilized in the prediction model (Aim 4). To determine the potential impact of overall physical activity in disease progression, all patients will be provided a Garmin activity monitor to measure overall daily activity (e.g., active minutes and steps per day). Currently, the Garmin activity monitor is utilized by 30,000+ participants in the CC Health System employee health plan, and accurately counts steps and activity levels of individuals with PD.³² Patients will wear the device on their belt/waistband or shoe during waking hours and upload the data every 30 days via the supplied application. Device batteries typically last ~6-months. To ensure no loss of data the battery will be replaced at the 6 month assessment. Activity monitor data will be synchronized with the secure CC Health system portal and downloaded to the [name] research server behind the CC firewall. The number of steps and minutes of activity, binned by day, week, month and year, will be considered for inclusion in the predictive model in Aim 4.

Leveraging a Widespread Consumer-based Home Exercise Platform: Our previous model of deploying a consumer-based interactive and connected exercise cycle to the home will be leveraged for this trial.²⁷ The Peloton Indoor Cycle (New York, NY) will serve as the platform to deliver the CYCLE exercise protocol and actively measure exercise performance variables. To ensure safety in exercising and understanding of the Peloton, exercise participants will be properly fit to the Peloton. [name] and [name] will be responsible for conducting this fitting session as both have extensive experience in fitting PD patients on exercise cycles. During this session seat height, reach, clipless or platform pedals, etc. will be optimized for comfort and safety in mounting and dismounting the cycle. Patients will complete a tutorial related to using the cycle, heart rate monitor and data transmission. Patients will be informed of their target HRR (Karvonen method: [(220-age)-resting HR] x 60-80% + resting HR) and complete a brief exercise session to ensure they fully understand the exercise requirements and Peloton interface. They will be provided a Garmin activity monitoring device and instructed on its use. Within 10 days of the clinical fitting session, a Peloton cycle will be delivered to the

Outcome Measure	Domain	Comprehensive
Aim 1		
MDS-UPDRS III	Rater-observed PD global motor symptoms	✓
Aim 2		
Nine Hole Peg Test	Upper extremity dexterity	✓
Timed Up & Go & 10M walk	Transfers, turning, gait speed	✓
Postural sway	Postural stability and Balance	✓
Self-reported falls	Prospectively recorded via fall diary	✓
Six Minute Walk Test	Cardiovascular fitness	✓
Aim 3		
Processing Speed	Info processing speed, implicit learning	✓
Visual Memory Test	Episodic Memory	✓
Trail Making Test A & B	Set-switching, attention, working memory	✓
Neuro-QoL	Quality of life questionnaire	✓
MDS-UPDRS I, II, IV	Part I: non-motor symptoms; Part II: self-reported motor symptoms; Part IV: motor complications	✓

patient's home by a certified technician. They will assemble and setup the cycle according to patient-specific fitting specifications. The certified technician will ensure all aspects of the cycle are working properly. The study coordinator will contact the patient within 48 hours of delivery to ensure the system is functioning as intended.

Standardized High-Intensity Home Exercise Program: The Peloton platform contains thousands of pre-recorded cycling classes with varying levels of intensities and recommendations. Study staff will select cycling protocols from this pre-recorded list for cyclists entering the study at different levels of fitness (beginners, intermediate, or advanced). Participants will be safely increased in RPMs, heart rate, and overall levels of perceived exertion over subsequent weeks of the study to reach study recommendations. Participants will be will be asked to exercise on the Peloton 3 times per week for 50-60 minutes (40 minutes at their target HRR + 5-10 minute warm-up and cool-down) for 12 months and encouraged to exercise using a relatively high cadence (80-90 rpms). To increase engagement, modules containing different professional Peloton instructors will be utilized. All instances of the modules will be similar in terms of aerobic intensity; however they will vary in type of background music and general personality of the instructor. In addition to the selected CYCLE modules, the patient will have the option to join more than 20 daily "live" sessions or select one of 300+ scenic courses on the Peloton platform. These additional options empower each patient to exercise in a manner best suited for them and will facilitate compliance. Considering the Peloton records, stores, and transmits heart rate, power, speed, estimated distance, time and cadence for every exercise session, regardless of whether the patient is completing a CYCLE module, live class or scenic ride, the specific module they complete is not critical as data are recorded, transmitted and downloaded to the study database regardless. Secure data transmission procedures are detailed in Protection of Human Subjects.

Study staff at each site will make bi-monthly calls to patients to address technology issues or compliance obstacles for those patients not meeting exercise recommendations. During these calls, exercise may be

progressed as deemed appropriate based on physiological signs monitored by the Peloton and patient subjective report (see Protection of Human Subjects for details).

Usual and Customary Care Group: Participants randomized to the UCC group will be asked to maintain their current exercise habits for 12 months. UCC can entail referrals to physical or occupational therapy or voluntary exercise. Due to the overwhelming evidence that those services are beneficial to individuals with PD, we will not restrict individuals from those programs. Similar to the home exercise group, a member of the study team will call these patients twice per month to inquire about activity levels, medication changes and technology assistance with the activity monitoring device and data.

Alternate Data Capture:

Due to the Covid-19 situation, the Cleveland Clinic and the University of Utah are requesting the ability to conduct virtual visits with participants. The Cleveland Clinic will utilize either FaceTime or Zoom, and the University of Utah will utilize the preferred platforms of their institution.

Inclusion/Exclusion Criteria:

Inclusion Criteria:

- a) Adult with a diagnosis of idiopathic PD by a physician or physician extender
- b) Hoehn and Yahr stage I-III
- c) Demonstrate the ability to safely mount and dismount the Peloton stationary cycle
- d) In-home WiFi (Peloton system requires WiFi to transmit exercise data)*

*2017 report indicates WiFi rates of 76% and 83% in Ohio and Utah households respectively

Exclusion Criteria:

- a) Participation in pharmaceutical or behavioral disease modifying PD-related clinical trial or study
- b) Diagnosis of dementia or any neurocognitive impairment that compromises one's ability to provide informed consent.
- c) Implanted deep brain stimulation electrodes
- d) Recommendation for medical clearance using the American College of Sports Medicine (ACSM) Preparticipation Health Screen (Figure 2)³³
 - a. If the ACSM screen recommends medical clearance, the subject must obtain medical clearance by their health care provider prior to participation.
 - b. Those who choose not to obtain physician clearance will not be eligible for participation. Those who do not receive physician clearance for high intensity exercise will not be eligible.
- e) A musculoskeletal issue (arthritis, osteoporosis, back problem) that would limit one's ability to engage in exercise
- f) Neurological disease other than Parkinson's disease (i.e. multiple sclerosis, Huntington's disease)
- g) Current or active cardiac arrhythmia
- h) DeNovo patients (have not begun Parkinson's disease medications).

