The distributions of baseline variables will be summarized, overall and by treatment group, by frequency distribution for dichotomous and other categorical factors, mean and standard deviation for reasonably symmetrically distributed quantitative variables, and Tukey five-number summaries (median, quartiles, extrema) for substantially skewed variables. We will also examine boxplots, histograms and kernel density estimators for continuous variables, and use standardized mean differences for continuous variables and categories of nominal and ordinal variables to describe balance of the randomized treatment groups.

Outcome description and distributional assessment

All prespecified outcomes are quantitative or potentially treatable as such depending on the degree to which their full scales occur in our study population. We will thus describe each initially as indicated above for quantitative baseline variables, overall and by treatment \times time combinations, including visually using grouped boxplots and kernel density estimators. To assess compatibility with the assumptions of the planned analytic approach, for each outcome we will use restricted (equivalently, residual) maximum likelihood (REML) estimation to fit preliminary mixed models with fixed effects of randomized treatment, visit, and their interactions, and with unrestricted covariance matrices -- thus allowing within treatment and visit variability to change over time and accounting for arbitrary correlations between measurements of the outcome in the same patient at different visits. These models will not be used to estimate treatment effects, but only to assess the compatibility of their residuals with the requisite distributional assumptions about random noise to support validity of fixed effect estimates and tests from the planned inferential analyses.

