For outcomes with distributional characteristics reasonably compatible with standard linear mixed model assumptions, we will employ prespecified linear mixed model analyses for the observations at baseline, six months, and twelve months, i.e., one year, as described below. For outcomes whose distributions, conditional on treatment and time, are substantially skewed and/or lighter or heavier tailed than Gaussian distributions (leptokurtotic or platykurtotic), we will consider applying the planned analysis to a Box-Cox and other reasonably straightforward data transformation of the outcome and backtransforming the results, and/or use of a generalized linear mixed model with log or other link function and/or a non-Gaussian exponential family or a beta error distribution. In exploring Box-Cox transformations, we will be generally guided by the independence pseudologlikelihood of the fitted fixed effects model saturated for treatment \times visit with clinical site as an additive covariate, as a function of the Box-Cox transformation power parameter. If and when transformations are used, we will report modeling results on the transformed scale and also report additive treatment effects, which for nonlinear transformations will vary by baseline value of the outcome, for selected percentiles of such baseline values. Nonparametric approaches such as quantile regression or product multinomial-based mixed categorical data models for marginal means will be considered as needed for bounded integer-scored outcomes with limited ranges and/or floor or ceiling effects, which may not admit of straightforwardly interpretable and communicable normalizing transformations.

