Once the scale of analysis and analytic approach have been chosen for outcomes incompatible with the prespecified default model, a covariance structure will be selected for each non-multinomial analysis by comparing Schwarz' Bayesian Information Criterion (BIC) after fitting the unconstrained fixed effects model above using the following six choices: time series homogeneous and heterogeneous order one autoregressive AR(1), order one antedependence, homogeneous and heterogeneous compound symmetry, and unrestricted. The homogeneous AR(1) will be considered the default if it yields close to the minimum BIC; otherwise, the structure with minimum BIC will be used. Residuals from the above saturated fixed effects model with the selected covariance structure will then be checked as above to confirm adequacy of the transformation or generalized linear mixed model.

Treatment effect estimation and testing

Assuming required assumptions are reasonably met, missing data will be multiply-imputed with 50 imputations, as described above, after any transformations of all outcomes to the respective scales determined for analysis. Treatment effects will then be estimated and tested by fitting mixed models, also as described above, on the original or transformed scale, but assuming equally spaced visits and linear time effects, to each imputed full data set. Estimates of the annual rate of change of the outcome variable within each treatment group, and of the treatment effect as their difference, with respective standard errors, will be obtained from each imputation and combined over all imputations using Rubin's standard method, yielding overall point estimates of the rates in each group and the difference in rates between the home Peloton-based exercise and usual care groups (i.e., the treatment effect), with respective overall 95% confidence intervals. Statistical significance of the treatment effects and of temporal change within each group will be tested using Wald statistics. Point and interval estimates on a transformed scale will be back transformed and reported and interpreted on the scales of the original measurements as differences between model-fitted (“predicted”) values of the outcomes for participants beginning with the same baseline value of the outcome measure but assigned to the two groups, for a selection of baseline percentiles of the outcome measure (e.g., 5, 10, 25, 50, 75, 90, 95)..

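### The treatment-effect model does not say whether site, the stratification factor, is included, and on neither reading does it contain site × time, although the effect is a difference in annual rates

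*Protocol*

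**What the plan says.** Under Participant Recruitment, Screening and Randomization, the protocol assigns patients "using a permuted block randomization stratified by site" and expects the two sites to enrol equally. The SAP Overview and its section Treatment effect estimation and testing make the treatment effect a difference between arms in annual rate of change.

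The model for that effect is given by cross-reference:

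- Outcome description and distributional assessment points forward: "we will employ prespecified linear mixed model analyses for the observations at baseline, six months, and twelve months, i.e., one year, as described below".
- Treatment effect estimation and testing points back: "Treatment effects will then be estimated and tested by fitting mixed models, also as described above, on the original or transformed scale", with one change, namely "assuming equally spaced visits and linear time effects".

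The earlier text offers two candidates. The first is the set of "preliminary mixed models with fixed effects of randomized treatment, visit, and their interactions". It has no site term, and the SAP adds: "These models will not be used to estimate treatment effects". The second is the treatment-by-visit model that guides the Box-Cox choice, which carries site as an additive term. The covariance-selection paragraph then mentions "Residuals from the above saturated fixed effects model with the selected covariance structure" without saying which of the two it means.

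Site appears in two other places: as a predictor in the imputation model (Missing Data), and in a treatment × site interaction examined only for outcomes with a significant effect (Effect modification/subgroup analyses).

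**The concern.** Two statisticians following this SAP could fit different primary models, one with site and one without. The same ambiguity carries to all nine inferential outcomes.

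Settling it in favour of an additive site term would not fully align the analysis with the randomisation. An additive term removes a difference in level between sites, whereas the treatment effect is a contrast of slopes. If patients at one site decline faster on average, that difference is left mostly in the residual variance. Stratified allocation has meanwhile balanced it between the arms, so the estimate itself is unaffected. The reported standard error is then larger than the true one. What is at stake is a little precision, and a primary model that can be read from the SAP without choosing between antecedents.

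**Working it through.** **Which model is meant.** The word "saturated" occurs before the covariance-selection paragraph only in the Box-Cox passage, where site is additive. That makes additive site the likelier reading, but it is not stated. Neither reading has site × time.

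**Could another section bring site in?** Sensitivity analyses considers adjustment for variables with a standardised difference above 15% or a variance ratio above 2.0. The protocol uses blocks of 8, 10 or 12 for the first eight blocks at a site and 4, 6 or 8 after that. Eight blocks hold at most 8 × 12 = 96 patients. With about 125 per site the open block is therefore at most 8, and the within-site imbalance at most 4. The worst case is +4 at one site and −4 at the other, so one site supplies 65/126 of one arm and 61/126 of the other. The standardised difference is (4/126) / √(65 × 61/126²) = 4/√3965 = 0.0635, about 6.4%, and the variance ratio is 1.0. This bound assumes equal enrolment. The treatment × site analysis would normally bring in site × time, but it follows a significant result and so cannot affect the primary test.

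**Size.** The documents give no figure to reproduce, so this is illustrative.

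- From the documents: two sites, 1:1 allocation, N about 250, visits at 0, 0.5 and 1 year, two-sided 5% test. On covariance, "The homogeneous AR(1) will be considered the default if it yields close to the minimum BIC".
- Assumed: d, the site difference in mean one-year change in within-site SDs of that change; adjacent-visit correlation 0.6, 0.75 or 0.9; complete data; 80% power for the correctly specified model.

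Each site's mean departs from the average by m = ±D·t/2, with D = d × SD(one-year change). With no site term, the AR(1) structure is fitted by Gaussian likelihood to the within-site covariance plus mm′. With additive site, the same is done after removing the generalised least-squares level from m. Let r be the resulting slope-contrast SE divided by that of the site × time model. Because arms are balanced within site, the true sampling SE does not change, so:

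- power = Φ(2.802 − 1.960r)
- equivalent extra participants = 250 × {[(0.842 + 1.960r)/2.802]² − 1}
- type I error = 2Φ(−1.960r)

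Example (no site term, d = 0.5, correlation 0.9): r = 1.0143. Power = Φ(2.802 − 1.988) = 79.2%. Participants = 250 × [(2.830/2.802)² − 1] = 5.0.

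| d | SE excess, additive site | SE excess, no site | Participants, additive | Participants, no site |
|---|---|---|---|---|
| 0 | 0 | 0 | 0 | 0 |
| 0.1 | 0.05–0.06% | 0.06% | <1 | <1 |
| 0.2 | 0.2% | 0.2% | <1 | <1 |
| 0.3 | 0.43–0.51% | 0.50–0.52% | 1.5–1.8 | 1.7–1.8 |
| 0.5 | 1.18–1.42% | 1.37–1.43% | 4.1–5.0 | 4.8–5.0 |
| 0.7 | 2.29–2.75% | 2.67–2.79% | 8.1–9.7 | 9.4–9.8 |

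With no site term, the power loss at d = 0.3, 0.5 and 0.7 is about 0.3, 0.8 and 1.5 points, and type I error is 4.9%, 4.7% and 4.4%.

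**Other covariance structures.** If compound symmetry is true and selected, the excess is 0.56%, 1.55% and 3.02% at d = 0.3, 0.5 and 0.7, with or without additive site. Under the unrestricted structure r = √(1 + d²/4), giving 1.12%, 3.08% and 5.95%. That is an upper bound only. In simulated trials with an AR(1) truth and no site term, the unrestricted structure had the minimum BIC in 0 of 1,500 at d = 0.5 and 7 of 1,500 at d = 0.7.

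**Check of the mechanism.** A separate simulation used N = 250, correlation 0.7, an unrestricted fit and a deliberately large d = 1.0. The model SE was 1.424 with no site and 1.427 with additive site, against an empirical SE of 1.293. With site × time it was 1.273 against 1.294.

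**The case against.** The best defence is that nothing in the documents suggests the sites differ in slope. They share eligibility criteria, visit schedule, off-medication testing and assessment battery, and a stable rater difference between sites would cancel out of a rate of change. Leaving out a precision covariate is valid, and the SAP says openly that it relies on randomisation. On the likelier reading, the stratification factor is already in the model. All of this stands. It limits the size of the point but does not remove the ambiguity about site.

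A reader might go further in four ways that the documents do not support:

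- *The model's fixed effects are never listed.* Treatment, time and treatment × time are recoverable from the earlier section; only site is unresolved. The statement that the preliminary models will not estimate effects does not stop their fixed-effect structure being reused. The SAP also cites a published design and analysis paper, not seen here, which may name the terms.
- *Site is nowhere more than additive.* This holds for the main treatment-effect model only, given the conditional treatment × site analysis.
- *Site can never reach the 15% threshold.* The 6.4% bound needs equal enrolment, which the protocol only anticipates. With a split such as 60/190, the smaller site could still be within its first eight blocks, with an imbalance of 6, and the standardised difference could reach about 10%. That is still below 15%, so site is unlikely to enter by that route.
- *The primary result could be biased or falsely positive.* Any error is in the conservative direction.

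**Conclusion.** The point holds as a minor specification gap with a nearly free gain in precision. Confidence is high that the text does not settle whether site is included and that the main model has no site × time term. Confidence in the size of the gain is low, because it depends wholly on an assumed site difference in slope. At 0.2 SD or less the loss is worth under one participant under AR(1). It reaches about 8–10 participants in 250 only if the sites differ by 0.7 SD. The figures also assume complete data, balanced arms within site and the default AR(1) structure. If the sites progress alike, nothing is lost by the present plan.

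**What to change.** In the SAP section Treatment effect estimation and testing, state the fixed effects for the primary and all secondary outcomes: treatment, linear time, treatment × time, site and site × time. Say that each arm's annual rate is reported averaged over sites. Leave the conditional treatment × site analysis under Effect modification/subgroup analyses as it is.

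The cost is one line of SAP text and two model degrees of freedom, or one if additive site is already intended. No change to data collection or sample size is needed.
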